### 11.7 Safety Analyses

The ITT population will be used for the analysis of safety data.

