#### ii. Safety

The secondary safety objectives of the study are:

- Determine the rate of post-surgical wound complications after pre-operative radiation and capecitabine among patients who undergo surgery
- Determine the rate of grade III toxicities (excluding acute skin toxicity)

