### **3.2 Pre-operative breast radiation alone**

Treatment of non-metastatic/oligometastatic IBC and locally advanced non-IBC consists of neoadjuvant chemotherapy, mastectomy and axillary lymph node dissection, followed by adjuvant radiation. In patients with progressive disease during neoadjuvant chemotherapy, widespread metastatic disease at presentation, and inoperable disease either at presentation or after neoadjuvant chemotherapy, or gross in breast/chest wall recurrence, pre-operative radiation is a component of appropriate standard of care to achieve tumor and symptom control and potentially render patients operable. Local control in 42 IBC patients treated at MDACC with pre-operative or definitive radiation for gross disease (40/42 without concurrent chemotherapy) was 75% at 5 years. Distant metastasis free survival was 20% with 8 patients alive without evidence of distant metastasis at  $\geq 40$  months of follow up (range among women alive without evidence of disease 40 – 240 months, unpublished data).

Among 38 non-IBC patients treated with radiation for inoperable breast cancer resistant to anthracycline-containing primary chemotherapy on five consecutive MDACC institutional trials without evidence of distant metastases at diagnosis revealed thirty-two (84%) of the 38 patients were able to undergo mastectomy after radiotherapy. For the whole group, the overall survival rate at 5 years was 46%, with a distant disease-free survival rate of 32%. The 5-year survival rate for patients who were inoperable because of primary disease extent was 64% compared with 30% for those who were inoperable because of nodal disease extent ( $p = 0.0266$ ). The 5-year rate of locoregional control was 73% for the surgically treated patients and 64% for the overall group. Of the 32 who underwent mastectomy, the 5-year rate of significant postoperative complications was 53%, with 4 (13%) requiring subsequent hospitalization and additional surgical revision. Preoperative radiation doses of  $\geq 54$  Gy were significantly associated with the development of complications requiring surgical treatment (70% vs. 9% for doses  $< 54$  Gy,  $p = 0.0257$ ).

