## **ii. Safety**

The secondary safety objectives of the study are:

- Determine the rate of post-surgical wound complications after pre-operative radiation and capecitabine
- Determine the rate of grade III toxicities (excluding acute skin toxicity)

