### **11.3 Sample Size Considerations and Interim Analyses**

The primary objective of this study is to determine the efficacy of pre-operative radiation with concurrent capecitabine in patients who have experienced a minimal response or progression after standard neoadjuvant chemotherapy. Efficacy will be determined by tumour response (complete response + partial response) as measured by RECIST criteria. Tumour response will be assessed after 45 Gy. Those who do not finish will be considered non-responders. Toxicity will be assessed at the same time. Surgical complications will be assessed independently within 6 weeks of surgery. Only grade three toxicity will be considered in the stopping rules. This study will be monitored for both efficacy and safety. Safety will be determined by the rate of grade 3 or higher toxicities, excluding acute skin toxicity. This regimen will not be considered of interest for further study if there is a high probability that the response rate is less than 80% or the severe toxicity rate is greater than 20%. Priors regarding response are based on combined retrospective data from three studies of 135 total patients treated for gross disease in the breast at our institution and detailed in the background (sections 3.2 and 3.5). Local control (a surrogate for response) at 5-years in patients treated for gross IBC disease in the breast with radiation alone was 75% (N = 42, unpublished). In 38 similar patients with non-inflammatory breast cancer local control was 70% at 5 years. In an unpublished retrospective analysis of 55 patients treated with the regimen proposed herein, 5-year local control was 85% (Perkins, SABCS abstract, 2007). There are limited and poor data regarding radiation alone toxicity in this exact cohort. The priors for toxicity were based on aggressive xrt in post-mastectomy patients (N = 192). In these patients, we expect a 15% rate of Grade 3 toxicities in patients receiving 60Gy and a 29% rate of Grade 3 toxicities in patients receiving 66Gy, and unpublished data. Clinically we are currently limiting the use of the latter regimen based on the impression that this is unacceptably high toxicity, so we are targeting a Grade 3 toxicity rate of no more than 20%. All patients who receive any treatment will be included in the analyses of both efficacy and safety. Patients who are not evaluable for response will be considered non-responders. The final analysis will be an Intent to Treat analysis. A total of 60 patients will be enrolled at the rate of 3-4 patients per month. Stopping boundaries will be assessed in cohorts of 5 patients after a minimum of 10 patients have been enrolled. Response and toxicity will be monitored independently. The method of Thall and Simon will be employed to perform interim monitoring.

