#### **11.5 Analysis Populations**

Analyses of both efficacy and safety will be performed in the intent-to-treat (ITT) population, and will comprise all patients who received at least one dose of the investigational product. The surgical population includes only subjects who underwent definitive surgery.

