#### **11.6 Efficacy Analysis**

The ITT population will be used for the primary analysis of both the efficacy and safety data. The surgical population will be used for a secondary analysis of the surgical efficacy data. Only patients who undergo both pre-treatment and post-treatment core biopsies will be considered in the primary translational analysis.

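### Wound complications are defined among operated patients, but section 11 puts all safety data on the all-treated population, which would lower the reported rate

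*Combined protocol and SAP*

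**What the plan says.** Two places state what is to be estimated, and they differ.

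- Section 1.0, safety objectives: "Determine the rate of post-surgical wound complications after pre-operative radiation and capecitabine among patients who undergo surgery".
- Section 10.0, safety endpoints: "Determine the rate of post-surgical wound complications after pre-operative radiation and capecitabine", with no condition on surgery. The secondary efficacy item in the same section does restrict itself to patients who go on to surgery.

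The analysis sections then name one population for safety, without exception.

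- Section 11.3: "All patients who receive any treatment will be included in the analyses of both efficacy and safety".
- Section 11.5 defines the ITT population as everyone who received at least one dose, and assigns efficacy and safety to it. Section 11.6 repeats the assignment.
- Section 11.7, in full: "The ITT population will be used for the analysis of safety data".

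A second population exists. Section 11.5: "The surgical population includes only subjects who underwent definitive surgery". Its only stated use is in section 11.6: "The surgical population will be used for a secondary analysis of the surgical efficacy data".

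On timing, section 11.3 says: "Surgical complications will be assessed independently within 6 weeks of surgery". Section 6.0 also has toxicity recorded by RTOG criteria at each follow-up visit, and does not say whether late wound events enter this endpoint.

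**The concern.** A wound complication can occur only in a patient who has had an operation. If the denominator is all treated patients, each unoperated patient counts as a success on an outcome that she could not have had. The figure then mixes two things: how often wounds break down, and how often patients reach surgery.

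Unoperated patients are part of the design. Section 1.0 includes palliative treatment in the primary objective. Section 6.0 has palliative or pre-operative intent recorded at entry and lets the treating oncologist change a pre-operative patient to palliative during treatment.

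The outcome matters to the protocol. Section 4.1 cites an earlier institutional series on surgical complications as its reason for limiting dose to potentially resectable disease. A wound rate lowered by its denominator would give a misleading picture of that risk.

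**Working it through.** **The plan's own figures.** The documents give no target, precision or sample size for wound complications, so there is no stated wound figure to reproduce. The nearest safety figure is in section 11.3.3: with 5 severe toxicities in 60 patients, a 95% credible interval of 3.1% to 16.8%. The prior beta(0.4, 1.6) gives the posterior beta(0.4 + 5, 1.6 + 55) = beta(5.4, 56.6), with limits 3.10% and 16.82%. This agrees. The denominator of 60 is right there, because every treated patient is at risk of toxicity from the regimen. That does not hold for wound complications.

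**Inputs.**

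- Sample size: 60 (section 11.3).
- Illustrative rates among operated patients, from section 3.2: "Of the 32 who underwent mastectomy, the 5-year rate of significant postoperative complications was 53" per cent; and 4/32 = 12.5% (printed as 13%) needing hospitalization and surgical revision.
- Historical shares: 32/38 = 84% had mastectomy (section 3.2); 91% of 55 became operable, and 23/28 = 82% became operable (both section 3.5).
- Share operated in this trial: not given. I assume 40-70% to allow for palliative-intent patients.

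**Formula.** All-treated rate = (number operated / 60) × rate among operated. The relative fall is one minus the share operated.

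| Share operated | Operated of 60 | 53% is reported as | 12.5% is reported as |
|---|---|---|---|
| 91% (historical) | 55 | 0.53 × 55/60 = 48.6% | 11.5% |
| 84% (historical) | 50 | 0.53 × 50/60 = 44.2% | 10.4% |
| 82% (historical) | 49 | 0.53 × 49/60 = 43.3% | 10.2% |
| 70% (assumed) | 42 | 0.53 × 42/60 = 37.1% | 8.75% |
| 40% (assumed) | 24 | 0.53 × 24/60 = 21.2% | 5.0% |

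The relative fall is 9-18% at shares of 91% to 82%, and 30-60% at shares of 70% to 40%.

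**Effect on the interval.** Suppose 30 of 60 patients are operated and 16 have a complication. Among operated patients the rate is 16/30 = 53.3%, exact 95% CI 34.3% to 71.7%. Among all treated it is 16/60 = 26.7%, CI 16.1% to 39.7%. The second interval is narrower and excludes the rate among operated patients. Only the denominator has changed.

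**The case against.** The strongest reply is that the specific objective in section 1.0 fixes the denominator and the one-line section 11.7 is generic. Even section 10 still says post-surgical. An analyst with the event count and the number operated could report the intended rate at once. This stands in part: the documents contradict themselves, and dilution follows only if section 11 is applied literally. But sections 11.3, 11.5, 11.6 and 11.7 all point the same way, and the population that would give the right denominator is reserved for efficacy. The analysis section is where an analyst looks, and there the instruction is wrong.

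A second reply is that the size is uncertain. That is fair. At the documents' historical shares the fall is modest. The larger falls rest on an assumed 40-70% operated.

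A reader might go further and infer that the 6-week window discards later complications, so that the trial's rate would be wrongly set against the 5-year 53%. The documents do not support this:

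- No section excludes wound events after 6 weeks, and section 6.0 records toxicity at every visit. The plan simply does not say whether late events count.
- No comparison with the 53% is planned. It is background, from non-inflammatory patients without distant metastases at diagnosis who were treated with radiation. This trial adds capecitabine and admits inflammatory and oligometastatic disease.
- Scheduled follow-up ends at about 33 months if the intervals are added (3 + 6 + 12 + 12), or about 24 months if they are read as time points. A 5-year rate is out of reach whatever the window.
- The share of complications arising after 6 weeks is not given, so a loss from the window cannot be calculated or combined with the denominator effect.

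The 53% is used above only as an illustrative rate.

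**Conclusion.** The point holds as a contradiction between the objective in section 1.0 and the analysis rules in section 11. Applied literally, those rules give the wrong rate for a secondary safety endpoint, always in the favourable direction. A true 53% would appear as about 43-49% at operated or operable shares of 82-91%, and as about 21-37% if 40-70% are operated. The first range assumes that this trial resembles the historical series, two of which report operability, not surgery performed. The second rests on a share that the documents do not supply.

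It should be corrected, but its reach is limited. The response endpoint, the stopping boundaries and the criteria in section 11.1 do not depend on it: section 11.3 assesses surgical complications separately from the monitored toxicity.

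**What to change.** 1. In sections 10 and 11.7, state that wound complications are analysed only in patients who had surgery after protocol therapy. Use the number operated as denominator and report an exact 95% confidence interval. This brings both sections into line with section 1.0. Add the same exception where sections 11.3, 11.5 and 11.6 assign safety to all treated patients.
2. State whether palliative operations are included. Section 11.5 limits the surgical population to definitive surgery, while section 6.0 can be read as also providing for palliative surgery. Pointing to the existing surgical population without comment could therefore omit some wounds.
3. Keep the 6-week assessment, and state whether wound events recorded at later visits are also reported.

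The cost is wording. No new patients or visits are needed. The downside is a less favourable rate on fewer patients: with 24 operated and 13 events, for example, 54.2% with an exact 95% CI of 32.8% to 74.4%. That width is the real precision available on this endpoint.
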